3.3 Biosample storage

We do not plan to undertake analyses of the biosamples within this project but will retain them for unspecified, future work to examine epigenetic and other 'omic changes in relation to firesmoke exposure. After collection and immediate processing, whole blood, serum and urine samples will be held in long-term storage in a dedicated freezer at -80° +/- 10° C, located in an HTA-compliant facility at Imperial.

4. PARTICIPANT RECRUITMENT

4.1 Recruitment strategy and pre-recruitment evaluations

On our behalf, to satisfy the requirements of GDPR, London Fire Brigade (LFB) will identify the names and contact details of all firefighters (c.1000) who directly attended the Grenfell Tower fire in June 2017; every effort will be made to include those who have left service since the fire, estimated to number no more than a dozen. We will also recruit, a sample (n=100) from a 'referent' group, those who were eligible to attend the fire but did not do so because of annual leave and the like. In order to conform to CONSORT, we will ask LFB to provide a breakdown, by age and sex, of all eligible to take part.

We will not undertake any pre-recruitment evaluations. Each potential participant will be invited, by the Brigade, to take part in an independent and confidential survey of (cardio) respiratory health, to

London

take place in the clinical research facility of Royal Brompton hospital in London; a proposed letter of invitation is attached. Up to two follow-up letters of invitation will be sent to those who do not respond to earlier invitations.

LFB have agreed to bear the costs of 'cover' at work for participants and of travel for those in current service. We will cover any travel costs for the small number of participants who have left service. We will not offer any other inducement. LFB will be aware of who has taken part in the study as they will need to ensure their work shifts are covered whilst they attend the study visits.

4.2 Inclusion Criteria

Attendance (or eligibility to attend) Grenfell fire as a firefighter

4.3 Exclusion Criteria

Unwillingness or inability to provide informed consent

4.4 Withdrawal Criteria

Participants will be free to withdraw at any stage without giving reason; they can do so prior to or at any time during the survey. Any data collected from them up the time of withdrawal will be used, as with fully participating individuals, only after (pseudo-)anonymization.

5. ADVERSE EVENTS

5.1 Definitions

Adverse Event (AE): any untoward occurrence in a participant.

Serious Adverse Event (SAE): any untoward and unexpected occurrence or effect that:

- results in death
- is life-threatening refers to an event in which the subject was at risk of death at the time of the event; it does not refer to an event which hypothetically might have caused death if it were more severe
- requires hospitalisation
- results in persistent or significant disability or incapacity

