5.2. Reporting Procedures

All adverse events will be reported. Any questions concerning adverse event reporting will be directed to the Principal Investigator in the first instance.

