5.2.1 Non serious AEs

All such events, whether expected or not, will be recorded.

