5.2.2 Serious AEs

An SAE form will be completed and emailed to the Principal Investigator within 24 hours. All SAEs will be reported to the Ethics and Research Governance Coordinator at Imperial where, in the opinion of the Principal Investigator, the event was:

• 'related', i.e. resulted from the administration of any of the research procedures; and

London

• 'unexpected', i.e. an event that is not listed in the protocol as an expected occurrence

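### Section 5.1 makes unexpectedness part of the SAE definition, so a serious but recognised reaction to a study procedure can miss the SAE form and its 24-hour limit

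*Protocol*

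**What the plan says.** Section 5.1 gives two definitions. The wider one carries no condition on expectedness: "Adverse Event (AE): any untoward occurrence in a participant". The narrower one, for serious events, does: an SAE is "any untoward and unexpected occurrence or effect that" leads to death, threatens life, needs hospital admission or leaves lasting disability.

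Three reporting rules follow.

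- Section 5.2, for everything: "All adverse events will be reported". It sets no form and no time limit, and it sends questions about reporting to the Principal Investigator.
- Section 5.2.1, for non-serious events: "All such events, whether expected or not, will be recorded".
- Section 5.2.2, for SAEs: "An SAE form will be completed and emailed to the Principal Investigator within 24 hours". Onward reporting is narrower: "All SAEs will be reported to the Ethics and Research Governance Coordinator at Imperial where, in the opinion of the Principal Investigator", the event was both related, meaning that it "resulted from the administration of any of the research procedures", and unexpected, meaning "an event that is not listed in the protocol as an expected occurrence".

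No list of expected occurrences appears in section 5 or elsewhere in the protocol text at hand.

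**The concern.** Seriousness, relatedness and expectedness are separate questions. Section 5.2.2 treats them that way: a serious event triggers a form, and the Principal Investigator then decides whether it was related and unexpected. Section 5.1 places the expectedness question ahead of the form, with no definition and no named person to answer it.

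The survey in section 3.1 includes forced spirometry before and after an inhaled bronchodilator, and venous blood sampling. If someone is admitted to hospital after one of these, staff may regard the event as a known effect of the procedure and therefore expected. Under the literal definition they would then have no SAE to report on the form. At stake is prompt notice of serious events that the study procedures may themselves have caused. The expectedness judgement also passes from the Principal Investigator, where 5.2.2 puts it, to whoever decides whether to start a form.

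**Working it through.** No arithmetic decides this point. The check is to follow one event through section 5: serious, caused by a study procedure, and a recognised effect of that procedure. The route depends on what *unexpected* means in 5.1.

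| Step | 5.1 read in the ordinary sense | 5.1 read with the list-based meaning of 5.2.2 |
|---|---|---|
| Adverse event (5.1)? | Yes; no expectedness condition | Yes |
| SAE (5.1)? | No; a recognised effect is not unexpected | Yes; nothing is listed, so every event is unexpected |
| Covered by 5.2.1? | No; that section is for non-serious events | No |
| Covered by the general rule in 5.2? | Yes, without form or time limit | Yes |
| SAE form within 24 hours (5.2.2)? | Not triggered | Triggered |
| Principal Investigator's test (5.2.2)? | Not reached by any stated route | Reached; reported onward if judged related |

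If 5.2.1 is stretched to cover every event that is not an SAE, the left-hand column changes only in that the event must also be recorded. There is still no form and no time limit.

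Two further steps show that the sections do not fit together.

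1. *Redundancy.* If every SAE is unexpected by definition, the pair of conditions in 5.2.2 (related and unexpected) reduces to related alone. A separate test of expectedness has a purpose only if some SAEs are expected, and 5.1 rules those out.
2. *No useful work under either meaning.* In the list-based sense, with no list, the word in 5.1 excludes nothing. In the ordinary sense it excludes exactly the serious events that are recognised effects, before 5.2.2 can consider them.

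*How many people this covers.* Section 3.2 assumes 80% participation among 100 heavily exposed and 900 less exposed firefighters: 0.80 × (100 + 900) = 800. It states no participation rate for the 100 referents. If none to all of them attend, the total is 800 to 900; the same 80%, as an assumption, would give 800 + 80 = 880. The protocol gives no rate of serious reactions, so these are counts of people examined, not of events lost.

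**The case against.** The strongest reply is that the protocol defines *unexpected* once, in 5.2.2, and that a word should carry one meaning throughout a section. Read so, with no list, every serious untoward event is unexpected, is an SAE and gets the form. Nothing is lost. This stands as a possible reading, and it means that the gap is not certain. It is not secured by the text: 5.1 comes first, does not define the word and does not refer forward, and 5.2.2 gives its definition only for the Principal Investigator's later decision.

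A reader might infer three stronger things, which the documents do not support.

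- *That 5.2.2 expressly sends the same event the opposite way.* It does not. It speaks only of SAEs, so an event excluded by 5.1 never enters it. If an event counts as expected under both sections, neither sends it to the governance coordinator. The outcomes diverge only when 5.1 is read in the ordinary sense and 5.2.2 by its list. The conflict is one of implication.
- *That the event escapes reporting altogether, or that the Principal Investigator never learns of it.* Section 5.2 still requires all adverse events to be reported. What is lost is the form, the 24-hour limit and an assured route to the 5.2.2 test.
- *That a known number of events, or the study's results, are affected.* No event rate is given, and nothing here touches the primary comparison of R5 across exposure levels or its power statement.

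It is also fair to say that this is an observational survey using tests chosen to be minimally invasive, so serious reactions may be few. That limits the size of the problem but does not make the definition right.

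**Conclusion.** Wrong as written, and worth correcting. Section 5.1 mixes expectedness into the definition of a serious event. It thereby makes the second test in 5.2.2 redundant and, on a natural reading, leaves a serious but recognised procedure reaction with no assigned form or deadline.

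The conclusion rests on two things: that staff may give *unexpected* its ordinary sense in 5.1, where it is undefined, and that the protocol contains no list of expected occurrences, which is true of the text at hand. If staff instead apply the list-based meaning throughout, the practical loss is nil and only the redundancy and the reference to an absent list remain. The size in events cannot be given from the document.

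**What to change.** - In section 5.1, delete *and unexpected*, so that an SAE is any untoward occurrence or effect that meets a seriousness criterion. Seriousness alone then triggers the form within 24 hours.
- Leave relatedness and expectedness to the Principal Investigator's judgement under section 5.2.2.
- Reconcile 5.2.2 with the missing list. Either list in section 5 the occurrences regarded as expected from the study procedures, or state that none is so regarded, in which case every SAE judged related goes to the governance coordinator.

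The cost is two deleted words and either one sentence or a short list. The downside is possibly a few more SAE forms. Sample size, data collection and analysis do not change.

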5.2. Reporting Procedures

All adverse events will be reported. Any questions concerning adverse event reporting will be directed to the Principal Investigator in the first instance.

5.2.1 Non serious AEs

All such events, whether expected or not, will be recorded.

5.2.2 Serious AEs

An SAE form will be completed and emailed to the Principal Investigator within 24 hours. All SAEs will be reported to the Ethics and Research Governance Coordinator at Imperial where, in the opinion of the Principal Investigator, the event was:

• 'related', i.e. resulted from the administration of any of the research procedures; and

London

• 'unexpected', i.e. an event that is not listed in the protocol as an expected occurrence

6. ASSESMENT AND FOLLOW UP

At this stage we are not planning any face-to-face follow up. However:

- a. we will seek permission to contact participants for follow up should that be scientifically justified.
- b. we are seeking permission to link, at any future date, participants' NHS numbers to routinely collected health data such as those collected on hospital admission, on cancer identification and on death; this too will require further funding and additional approval from an ethics committee but we would not seek further permission to do so from individual participants.
- c. we are asking permission to analyse their biosamples at a future date; this will require further funding and additional approval from an ethics committee but, again, we would not seek further permission to do so from individual participants.

7. REGULATORY ISSUES

7.1 Ethics approval

The Principal Investigator has obtained approval from the Head of Department and will do so from the Joint Research Compliance Office (JRCO) at Imperial and from a national Research Ethics Committee (IRAS). The study will be conducted in accordance with the recommendations for physicians involved in research on human subjects adopted by the 18th World Medical Assembly, Helsinki 1964 and later revisions.

7.2 Consent

Signed consent to take part in the study will be sought from each participant only after an information leaflet (attached) has been offered, a full explanation has been given, and time allowed for consideration. The right of the participant to refuse to participate without giving reasons will be respected; all participants will be free to withdraw at any time. We do not anticipate that there will be any participants without a good understanding of spoken and written English or with other special communication needs

7.3 Confidentiality

The Principal Investigator will preserve the confidentiality of participants taking part in the study and fulfil transparency requirements under the General Data Protection Regulation for health and care research. Data and all appropriate documentation will be stored for a minimum of 10 years after the completion of the study.

7.4 Indemnity

Imperial College London holds negligent harm insurance policies which apply to this study.

7.5 Sponsor

Imperial College London will act as the main Sponsor for this study

7.6 Funding

The funding for the initial stage of this study is provided by the COLT Foundation. Neither participants nor investigators will receive direct payment for the study.

7.7 Audits

The study may be subject to inspection and audit by Imperial College London under their remit as sponsor and other regulatory bodies to ensure adherence to GCP and the UK Policy Framework for Health and Social Care Research.

8. STUDY MANAGEMENT

The day-to-day management of the study will be co-ordinated through [name]. She will liaise regularly and frequently with [name].

9. PUBLICATION POLICY

The goal of the study's publication policy is to disseminate accurate and informative results of the research to the scientific community and to other interested stakeholders; these results include those of primary study outcomes, secondary analyses, and ancillary studies. Priorities in selecting forums for publication will be given to peer-reviewed journals as well as presentations and publications of abstracts at national and international scientific meetings. The PIs will work with the study statistician to identify potential scientific papers related to both the study's primary and secondary aims, establish writing teams and manuscript authorship, and prioritize manuscript development. The PIs will write the scientific manuscripts related to the study's primary aims as lead/senior author(s). The lead author will be responsible for assuring production of the draft of the paper within three months of availability of the data. This time period should allow for review and comment of the draft by all co-authors and input from other members of the study team. For protocols that have secondary research aims, investigators other than the PIs may be assigned lead authorship of manuscripts. Investigators who accept lead authorship of manuscripts related to secondary aims will be expected to produce a manuscript of publishable quality following the principles outlined above. Abstracts reporting the preliminary or highlighted results of the research will not negate the necessity of preparing a full manuscript for publication. All papers and abstracts will be submitted to LFB for their (timely) comment prior to submission; Imperial College retains the right to publish material without requiring the permission of LFB or any other external parties.

Material – written or audiovisual – that is intended for non-scientific audiences will be prepared by the PIs in conjunction with the study statistician and in consultation with LFB and, if deemed appropriate by them, the FBU; all such material must be agreed by all parties before its use.

No publications/presentations/press releases etc arising from this research will be produced in a manner that could identify any individual participant(s).

